7.7.1.1 Primary Analysis

In response to the anticipated variations in the sample sizes and data variables collected for these 13 clinical trials, there will be a primary analysis and a subsequent sensitivity analysis to avoid the introduction of extra-variation to the pooled data. The primary analysis will consist of all studies that meet the eligibility criteria with an adequate sample size of at least 20 subjects and at least 80% completeness of data for each variable in [List 1](#) (Table 2). This yields 5 clinical trials for K monotherapy totaling 564 subjects and 6 clinical trials for Kd totaling 1,199 subjects.

Table 2. Clinical Trials for Primary Data Analysis

K27 (540 subjects)	K56 (24 subjects)	Kd27 (583 subjects)	Kd56 (616 subjects)
20140119 (78 subjects)	20130393 (24 subjects)	20140355 (235 subjects)	20160275 (153 subjects)
20140118 (200 subjects)		20140242 (123 subjects)	20130398 (463 subjects)
20130396 (157 subjects)		20140120 (20 subjects)	
2011-002 (105 subjects)		2011-002 (205 subjects)	

7.7.2 Planned Method of Analysis

Data from these clinical trials will be pooled for the analysis of clinical parameters that may inform the choice of K dose regimen. Given the anticipated heterogeneity of sample sizes from early phase 1 and robust phase 3 studies and evolving data collection, a primary analysis and a subsequent sensitivity analysis will be performed. The primary analysis will consist of studies with an adequate sample size of at least 20 subjects and at least 80% completeness of data for each variable (List 1) to avoid introduction of extra-variation to the pooled data. In contrast, the sensitivity analysis will consist of all pooled data. For a detailed description of the efficacy and safety analyses, please refer to Section 7.7.2.4 and Section 7.2 of the SAP.

7.7.2.1 General Considerations

All analyses will be descriptive. No formal hypothesis testing is planned for the efficacy and safety comparison between carfilzomib dosing regimens (Kd27 versus Kd56; K27 versus Kd27).

7.7.2.2 Missing or Incomplete Data

The descriptive statistics will identify the extent of missing data. Rules for handling incomplete or missing data related to endpoints are detailed in the SAP of each individual trial. For this analysis, no imputation will be done for the analysis of the safety endpoints and efficacy endpoints. The handling of incomplete or missing dates for adverse events and death are also detailed in the SAP of each individual trial. For this analysis, the missing values for the continuous clinical parameters, or covariates, will not be imputed. The missing values for categorical covariates in each individual trial will be classified into a category called Unknown.

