7.2.2 Matching

The propensity score matching approach for the comparison of outcomes among carfilzomib regimens is detailed in Section 9.5.2.1 of the SAP. Briefly, to generate the propensity score for each subject, all the variables or covariates specified in [List 1](#) will be included in the propensity score model (logistic regression model) with the dosing regimen as the binary response. There will be propensity score matching for the datasets of Kd27 versus Kd56 and for K27 versus Kd27. For the evaluation of these

secondary and exploratory objectives, the propensity score matching creates mutually exclusive sets of observations that have similar propensity scores. The Greedy nearest neighbor 1:1 matching without replacement will be used to sequentially match each subject in the Kd56 regimen with one subject in the Kd27 regimen if the difference in the logits of the propensity score for pairs of subjects from the two groups is less than or equal to 0.1 times the pooled estimate of the standard deviation (Austin, 2014). The threshold 0.1 was chosen so that the resulting matched samples have balanced distributions of baseline covariates. Same method will be used to create a propensity score matched samples for subjects with Kd27 or K27.

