7.3 Variables

Selection of current treatments depend on a plethora of clinical parameters that vary in important and might affect the choice of K regimen for a particular patient. Given that the benefit-risk assessment is a cornerstone of decision making in medicine, and benefit-risk assessment is based upon efficacy outcomes and safety outcomes ([Reaney et al, 2019](#); [Curtin et al 2011](#)), special consideration will be given to clinical parameters known to impact efficacy and safety outcomes. Further consideration will be given to those clinical parameters that may be unique to efficacy and safety outcomes in those treated with carfilzomib. Specified below are the clinical parameters for analysis (List 1) for efficacy outcomes such as progression-free survival (PFS) and objective response rate and safety outcomes such as fatalities, grade 3 or higher AEs of special interest for carfilzomib, and serious AEs of special interest for carfilzomib. Variables common to both efficacy and safety outcomes are listed first. Further details are specified in the SAP.

List 1. Planned Variables to be Analyzed that May Inform the Choice of Carfilzomib Dosing Regimen

Variables for efficacy outcomes	Variables for safety outcomes
Age	Age
Gender	Gender
Race	Race
Ethnicity	Ethnicity
Body mass index	Body mass index
ECOG* performance status	ECOG performance status
Creatinine clearance	Creatinine clearance
Time from initial diagnosis	Diabetes
Stage of disease (International Staging System)	Dyslipidemia/hypercholesterolemia
Lactate dehydrogenase	Hypertension
Presence of plasmacytoma	Left ventricular hypertrophy
Number of prior lines of therapy	Chronic kidney disease
Prior stem cell transplant	Coronary artery disease
Prior exposure to lenalidomide	Year of treatment initiation
Prior exposure to bortezomib	
Refractory to lenalidomide	
Refractory to bortezomib	
Refractory to last treatment	
Time from last relapse or last treatment	
Year of treatment initiation	

* Eastern Cooperative Oncology Group

7.3.1 Rationale of Variables Pertaining to Subject Characteristics: Age, Gender, Race, Ethnicity, Body Mass Index, ECOG Performance Status, Creatinine Clearance

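### Continuous covariates are not imputed yet all enter the propensity model, so subjects missing one drop out of the matched comparisons, and the per-variable 80% floor does not bound their joint loss

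*Protocol*

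**What the plan says.** Four statements in the protocol bear on this.

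- Section 7.7.2.2 (Missing or Incomplete Data), on continuous covariates: "the missing values for the continuous clinical parameters, or covariates, will not be imputed". It makes no exception for the propensity model.
- The same section, on categorical covariates: "The missing values for categorical covariates in each individual trial will be classified into a category called Unknown".
- Section 7.2.2 (Matching): all List 1 covariates "will be included in the propensity score model (logistic regression model) with the dosing regimen as the binary response". Matching is greedy nearest-neighbour, 1:1, without replacement and within a caliper. Further detail is deferred to SAP Section 9.5.2.1.
- Section 7.7.1.1 (Primary Analysis): a study enters the primary set if it has at least 20 subjects and "at least 80% completeness of data for each variable in" List 1. Section 7.7.2 repeats the rule. It selects studies; no rule covers how complete an individual subject's record must be.

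Section 7.9.2 names two limits of the matching: subjects left unmatched and covariates not observed. It does not mention subjects lost because a covariate is missing.

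**The concern.** An ordinary logistic model returns no predicted probability for a subject with a missing continuous predictor. Without a score there is no match. Taken together, the rules make the matched comparisons complete-case analyses with respect to the continuous covariates, and the protocol does not say so. They also treat subjects unequally without a stated reason: a missing category keeps the subject in, a missing measurement puts the subject out.

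The matched comparisons carry the secondary and exploratory objectives, including Kd27 against Kd56. In Table 2 the Kd27 subjects come from studies 20140355, 20140242, 20140120 and 2011-002, and the Kd56 subjects from 20160275 and 20130398. No study supplies both. Any difference between studies in data capture is then a difference between regimens, and it acts before the matching that is meant to balance them. For K27 versus Kd27, only 2011-002 supplies both arms. The protocol itself expects uneven capture: Section 7.7.2 refers to evolving data collection, and Section 7.9.3 to studies spread over nearly a decade.

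**Working it through.** **The plan's own counts (Table 2).**

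- K27: 78 + 200 + 157 + 105 = 540
- Kd27: 235 + 123 + 20 + 205 = 583
- Kd56: 153 + 463 = 616
- K56: 24
- Totals: 540 + 24 = 564 for monotherapy and 583 + 616 = 1,199 for Kd, as stated

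The study counts equal the eligible counts in Table 1, so nothing has been deducted for missing covariates. The protocol gives no number of subjects expected to be scored or matched.

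**Assumptions.** The protocol does not say which List 1 covariates enter as continuous. I take five that are continuous by nature and could be missing: body mass index, creatinine clearance, time from initial diagnosis, lactate dehydrogenase, and time from last relapse or last treatment. Each has completeness c. Age, number of prior lines and year of treatment initiation are also numeric but are left out.

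**Formulas.** With k continuous covariates, the share of subjects without a score is:

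- full overlap (the same subjects miss everything): 1 − c
- independent missingness: 1 − c^k
- no overlap: the smaller of 1 and k(1 − c)

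**Results for k = 5.**

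| Completeness of each | Full overlap | Independent | No overlap |
|---|---|---|---|
| 80% | 20% | 1 − 0.328 = 67.2% | 100% |
| 90% | 10% | 1 − 0.590 = 41.0% | 50% |
| 95% | 5% | 1 − 0.774 = 22.6% | 25% |
| 98% | 2% | 1 − 0.904 = 9.6% | 10% |

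The result depends on k. At 80% with independence the loss is 48.8% for k = 3 and 83.2% for k = 8.

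**Subjects left with a score (k = 5).**

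| Completeness, pattern | Kd27 of 583 | Kd56 of 616 | K27 of 540 |
|---|---|---|---|
| 80%, full overlap | 466 | 493 | 432 |
| 80%, independent | 191 | 202 | 177 |
| 95%, independent | 451 | 477 | 418 |
| 98%, independent | 527 | 557 | 488 |

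The smaller arm caps the number of 1:1 pairs. For Kd27 versus Kd56 the cap falls from 583 to 466 or 191 at the floor, and to 451 or 527 in the last two rows. The caliper can only lower it further.

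**Unequal loss by regimen (assumed example).** If the Kd27 studies had 90% completeness on each covariate and the Kd56 studies 98%, independence would leave 583 × 0.590 = 344 Kd27 subjects (41.0% lost) and 616 × 0.904 = 557 Kd56 subjects (9.6% lost). Both pass the floor.

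**The case against.** The strongest reply is that the size is unknown and could be small. Nothing shows that any study sits near 80%. Section 7.4 describes source data verification, and Section 7.3.1 calls creatinine clearance an important eligibility criterion in myeloma trials. Covariates may also enter the model in categories: Sections 7.7.2.4 and 7.7.2.5.1 form subgroups from List 1, so grouped versions of at least some will exist, and a grouped covariate falls under the Unknown rule and loses nobody. The SAP was not available to settle this. All of this stands, and it is why the figures are only illustrations.

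The floor also protects. A study that largely failed to record a variable is out of the primary set, and Section 7.9.3 drops parameters expected to be mostly absent. In the retained studies, missingness on any one variable can differ between regimens by at most 20 percentage points. That limits each variable, not the combination.

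Two stronger readings are tempting. One is that the floor permits a loss of 20% to 67%. Those figures need exactly five continuous covariates, each at exactly 80%, with full overlap or independence. The rule itself allows anything from 0% (complete data) to 100% (five covariates at the floor with no overlap). The other is that the matched estimates will be biased. Complete-case loss costs precision and may change the population described, but it biases the contrast only under some missingness mechanisms, and the protocol demonstrates none.

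Nor is the missingness hidden: Section 7.7.2.2 has the descriptive statistics report its extent. What is absent is a count of subjects dropped before scoring.

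Finally, the analyses are descriptive, with no hypothesis test and no power target. That lowers the stakes, but hazard, odds and risk ratios from a selected subset can mislead without a test attached.

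**Conclusion.** The mechanism holds on the protocol's own text: no imputation of continuous covariates, every List 1 covariate in one logistic model, and a floor set per variable only. Subjects missing a covariate entered as continuous leave the Kd27 versus Kd56 and K27 versus Kd27 comparisons, and the protocol neither acknowledges nor bounds that loss.

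Its size cannot be read from the protocol. For five assumed continuous covariates it runs from 2% (98% complete, full overlap) to 67% (80% complete, independent), and beyond that if missingness does not overlap. It is nil if those covariates are complete or categorised. The loss can differ between regimens because study and regimen do not overlap for Kd27 and Kd56. Reduced precision follows from any loss; selection bias is possible but not shown. The primary objective describes each regimen without a propensity score and is not affected. Nor does the sensitivity analysis in Section 7.7.2.5 clearly help: it is described for the primary endpoint and drops the completeness floor.

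This should be fixed, but it does not invalidate the plan.

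**What to change.** Amend Section 7.7.2.2 for the matched analyses so that subjects with missing continuous covariates are retained.

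- **Preferred:** multiply impute the missing List 1 covariates, with trial and outcome in the imputation model; score and match within each imputed set; pool the estimates.
- **Minimum:** enter a fill-in value (for example the median) plus a missing indicator in the propensity model, which mirrors the Unknown rule.
- **Sensitivity:** keep the complete-case match.
- **Reporting:** tabulate, by trial and regimen, the subjects lost before scoring and those lost at matching.

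All 583 Kd27, 616 Kd56 and 540 K27 subjects could then be scored, provided no other rule removes them.

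The cost is protocol and SAP wording and more programming; no new data are needed. Multiple imputation assumes the values are missing at random given what is in the model. The indicator method balances the observed values and the pattern of missingness, not the unseen values, and may leave subjects hard to match if missingness is concentrated in one regimen.

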7.7.2.3 Descriptive Analysis

All analyses will be descriptive. Descriptive statistics will be produced to describe the exposure to carfilzomib by treatment group.

- Duration of treatment (weeks) defined as duration (in weeks) (the date of last dose of carfilzomib – the date of first dose of carfilzomib +1) / 7
- Number of carfilzomib administrations
- Cumulative dose received of carfilzomib (mg/m²) across all cycles
- Average dose received of carfilzomib (mg/m²): defined as the cumulative dose received divided by the number of doses administered

7.7.2.3.1 Description of Study Enrollment

The subjects will be enrolled based on eligibility criteria outlined in [Section 7.2.1](#) and from clinical trials summarized in [Table 1](#).

7.7.2.4 Analysis of the Primary, Secondary, and Exploratory Endpoint(s)

For the primary endpoint, the analyses will describe the distribution of each clinical parameter and the distribution of each efficacy/safety outcome by each dosing regimen (K27, Kd27, K56, and Kd56) to yield a summary of the favorable versus unfavorable effects for each dosing regimen.

For the secondary and exploratory endpoints, the outcomes for efficacy will use the well-established endpoints of PFS, an approved surrogate marker of overall survival, and ORR, one of the most commonly used endpoints in myeloma clinical trials. Each individual trial will follow its own definition of PFS and ORR, which was specified in its respective SAP, to derive these pooled data. For analyses of PFS, Kaplan-Meier estimates will be used to estimate the median and other quartiles along with corresponding two-sided 95% confidence intervals. For analyses of ORR, the associated 95% exact binomial confidence interval (Clopper-Pearson method) will be

reported for Kd56 versus Kd27 and Kd27 versus K27. Risk ratio (RR) with the corresponding 95% CIs for Kd56 versus Kd27 and Kd27 versus K27 will be estimated using Cochran-Mantel-Haenszel (CMH) method. To account for potential differences in drug exposure duration, exposure-adjusted incidence rate with the corresponding 95% CI will also be calculated.

Also, for the secondary and exploratory endpoints, outcomes for safety will use endpoints of all fatal events as well as grade 3 or higher and serious adverse events (AEs) of special interest (List 2). Classification of the severity of AEs from each trial will be in accordance with the NCI-CTCAE criteria used during that individual clinical trial, which was also specified in its respective SAP. The number and percentage of subjects experiencing the treatment-emergent adverse event (TEAE) by system organ class/preferred term (SOC/PT) will be summarized for the specified safety outcomes and presented side-by-side for the 4 dosing regimens (K27, K56, Kd27, Kd56) overall for both the primary and sensitivity analyses.

List 2. Adverse Events of Special Interest (in alphabetical order)

- Acute renal failure (SMQN)
- Cardiac events (Sum of events for cardiac failure [SMQN] + ischemic heart disease [SMQN] + torsades des points including QT prolongation [SMQB])
- Cardiac failure (SMQN)
- Hypertension (SMQN)

Clinical review for identification of AEs of special interest for this post-hoc analysis spanned the following types of events, in alphabetical order: cardiac, gastrointestinal, haematological (cytopenias), infusion reactions, peripheral neuropathy, pulmonary, renal, tumor lysis syndrome, and viral infections. Specific AEs of special interest consistently identified throughout the individual clinical trials were as follows (SMQNs unless otherwise specified): acute renal failure, cardiac arrhythmia, drug-related hepatic disorder, dyspnea (HL), embolic and thrombotic events – venous, hemorrhage, hepatic failure/fibrosis and cirrhosis/other liver damage-related conditions, hypertension, interstitial lung disease, ischemic heart disease (SMQB), liver related investigations - signs and symptoms, malignant or unspecified tumors, myocardial infarctions (SMQB), pulmonary hypertension, thrombocytopenia (SMQB), and torsade de pointes – QT prolongation (SMQB) (Carfilzomib Investigator's Brochure, 2019). However, AEs of special interest identified for this pooled analysis reflect the AEs of special interest consistently identified in individual clinical trials with increased incidence compared to

the control cohort without K or were notable in safety reports. This approach should capture AEs that lead to non-fatal treatment discontinuations for K, even if the overall incidence for that AE was low. Although thrombocytopenias occur in more than 20% of individuals treated with K, nearly all treatments for MM induce myelosuppression ([Package inserts for Cyclophosphamide, 2013](#); [Darzalex, 2016](#); [Empliciti, 2015](#); [Pomalyst, 2017](#); [Revlimid, 2017](#); [Sarclisa, 2020](#); [Thalomid, 2014](#); [Velcade 2008](#)) and supportive measures (eg platelet transfusions) are part of standard-of-care practices, making thrombocytopenia a less critical clinical parameter that may inform the choice of K dose in the RRMM setting. In other words, [List 2](#) focuses on those AEs that has the potential to directly impact the benefit-risk profile for K and thereby inform the choice of K dose regimen.

For the secondary and exploratory endpoints, each propensity score analysis will compare the efficacy (Hazard Ratio (HR)(CI) for PFS and Odds Ratio (OR)(CI) for ORR) and safety outcomes (Risk Ratio (RR)(CI)) overall and in subgroups determined by the clinical parameters from [List 1](#) (covariates). Based on the results, the favorable versus unfavorable effects of Kd27 versus Kd56 and K27 versus Kd27 will be summarized. The comparison of K27 versus K56 will not be included due to the limited sample size of the K56 cohort.

For further details, please refer to Section 9.5 and 9.6 of the SAP.

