6.1 Primary

Describe the benefit-risk profile for each pre-specified K regimen (K27, Kd27, K56, Kd56) based on the clinical parameters that are associated with efficacy and safety outcomes from the pooled data meeting the criteria for sample size and completeness of covariates

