7.6.2 Review and Verification of Data Quality

The database of each individual clinical trial was subject to edit checks outlined in the data management plan. Data inconsistencies and suspicious values were reviewed and resolved before the database was locked for analyses in clinical study report. The analysis datasets and variables in each individual clinical trial had been validated by sponsor. In this pooled study, each individual trial will follow its own derivations of the endpoints and variables, which are specified in its own SAP.

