20130401 (CFZ001)	An Open-label, Single Arm, Phase 1 Study of the Pharmacokinetics and Safety of Carfilzomib in Subjects with Relapsed Multiple Myeloma and End-stage Renal Disease	Relapsed or refractory MM; ≥ 1 prior tx; normal renal function or ESRD on hemodialysis	Phase 1, comparative PK with 2 cohorts based on CrCL	Assess influence of ESRD on AUC	Carfilzomib + dexamethasone K 20/27/56 mg/m ² (30 min) dex 8 mg BIW	K27: 4 subjects K56: 19 subjects Kd56: 3 subjects
20130398 (2011-003)	A Randomized, Open-label, Phase 3 Study of Carfilzomib Plus Dexamethasone Versus Bortezomib Plus Dexamethasone in Patients With Relapsed Multiple Myeloma (ENDEAVOR)	Relapsed MM; 1 to 3 prior tx	Phase 3, randomized, active-control	Efficacy; safety	Carfilzomib + dexamethasone vs bortezomib (V) + dexamethasone K 20/56 mg/m ² (30 min) dex 20 mg V 1.3 mg/m ²	Kd56: 463 subjects
20130396 (PX-171-011)	A Randomized, Open-label, Phase 3 Study of Carfilzomib vs Best Supportive Care in Subjects with Relapsed and Refractory Multiple Myeloma (FOCUS)	Relapsed and refractory MM; ≥ 3 prior tx	Phase 3, randomized, active-control	Efficacy; safety	Carfilzomib vs best supportive care K 20/27 mg/m ² (10 min) Corticosteroid (prednisolone 30 mg or dex 6 mg every other day) Optional CYC 50 mg QD	K27: 157 subjects

Footnotes defined on next page of the table

Table 1. Summary of Individual Clinical Trials to Derive Subject Data for Pooled Analysis

Study Number	Study Title	Subject Population	Design	Objectives	Drug Combination/ K Dose Schedule ^a	Eligible Subjects (K regimen: subject #)
20130393 (PX-171-007)	Phase 1b/2, Multicenter Open-label Study of the Safety and Activity of Carfilzomib in subjects with Relapsed Solids Tumors, Multiple Myeloma, or Lymphoma	Relapsed or refractory MM; ≥ 2 prior tx	Phase 1b/2, dose escalation	Safety and tolerability	Carfilzomib 20/36 to 20/70 mg/m ² (30 min)	K56: 24 subjects Kd56: 8 subjects
					Carfilzomib + dexamethasone K 20/45 or 20/56 mg/m ² (30 min)	
2011-002	Carfilzomib Multiple Myeloma Expanded Access protocol (C-MAP) for Subjects with Relapsed and Refractory Disease (C-MAP)	Relapsed or refractory MM; ≥ 4 prior tx; unable to enroll in another US CFZ study	Phase 2, single arm; expanded access program	Safety	Carfilzomib 20/27 mg/m ² (10 min)	K27: 105 subjects Kd27: 205 subjects

Page 5 of 5

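### PFS and ORR are pooled under each trial's own definition although Kd27 and Kd56 share no trial, and the entry criteria do not cover the completeness of these outcomes

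*Protocol*

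**What the plan says.** Section 7.7.2.4 sets the efficacy endpoints for the secondary comparison (Kd27 versus Kd56) and the exploratory one (K27 versus Kd27): "Each individual trial will follow its own definition of PFS and ORR, which was specified in its respective SAP, to derive these pooled data". Section 7.6.2 extends this to all derivations: "each individual trial will follow its own derivations of the endpoints and variables, which are specified in its own SAP". Sections 7.3.5 and 7.4 say the same. The propensity-matched comparisons then report a hazard ratio for PFS and an odds ratio for ORR, each with a confidence interval, overall and in subgroups.

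On missing endpoint data, Section 7.7.2.2 first says: "Rules for handling incomplete or missing data related to endpoints are detailed in the SAP of each individual trial". It then says that for the pooled analysis "no imputation will be done for the analysis of the safety endpoints and efficacy endpoints". On the amount of missing data it says only: "The descriptive statistics will identify the extent of missing data". No threshold or consequence is attached.

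To enter the primary analysis, a trial needs at least 20 subjects and "at least 80% completeness of data for each variable in" List 1 (Section 7.7.1.1). List 1 holds baseline parameters and no outcome. Section 6.1 agrees: the profile is described "from the pooled data meeting the criteria for sample size and completeness of covariates". Table 1 gives the design of study 2011-002 as "Phase 2, single arm; expanded access program", and safety is its only listed objective.

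**The concern.** Pooling trial-defined endpoints does little harm when each trial contributes to both sides of a comparison, because a definition then affects both sides. Here the main comparison has no trial on both sides. If the Kd27 trials and the Kd56 trials differ in when the PFS clock starts, how they censor, or whom they count in the ORR denominator, that difference appears as a dose effect. The propensity score model uses List 1 covariates measured before treatment. It can align who is compared but not how the outcome was defined.

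The completeness rule adds a second exposure. A trial can pass it on covariates and still have thin response or progression data. Study 2011-002 raises the question most sharply, given its size and its listed objective.

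The study is labelled descriptive, but its results are to be summarised as favourable or unfavourable effects of one regimen against another, to inform the choice of dose, and Section 11 says the report goes to the FDA as a regulatory requirement. An artefact of definition would be read as information about dose.

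**Working it through.** **1. Reproduce the pool sizes (Table 2).**

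| Regimen | Sum of trials | Stated |
|---|---|---|
| K27 | 78 + 200 + 157 + 105 = 540 | 540 |
| Kd27 | 235 + 123 + 20 + 205 = 583 | 583 |
| Kd56 | 153 + 463 = 616 | 616 |

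**2. Trials shared between regimens.**

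- Kd27: 20140355, 20140242, 20140120, 2011-002. Kd56: 20160275, 20130398. None is shared. In the wider pool of Table 3 (5 trials against 4) there is again none.
- K27 and Kd27 share 2011-002 in Table 2. In Table 3 they also share 20140120 and 20140122.

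Trial, and with it endpoint definition, is thus fully confounded with dose for Kd27 versus Kd56, and partly confounded with regimen for K27 versus Kd27.

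**3. Design of the contributing trials (Table 1).** Single-arm studies in Kd27: 20140242 (123), 20140120 (20) and 2011-002 (205). 123 + 20 + 205 = 348, and 348/583 = 59.7%. Both Kd56 trials are randomised phase 3. A single-arm study has no randomisation date from which PFS could start; a randomised trial has one. A difference in PFS start is therefore plausible, though not documented.

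**4. Share of 2011-002 before matching.** Kd27: 205/583 = 35.2%. K27: 105/540 = 19.4%. Kd56: none. Without it, Kd27 would be 583 − 205 = 378 and K27 540 − 105 = 435.

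**5. Illustration A: denominators differ.** Assumptions, not in the protocol: both regimens have true ORR p; one side's trials exclude a fraction d as non-evaluable, all of them non-responders; the other side's trials count them as non-responders. The first side then shows ORR p/(1 − d), and the spurious odds ratio is (1 − p)/(1 − p − d).

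- p = 0.50, d = 0.10: ORR 0.50/0.90 = 55.6%; OR = 0.50/0.40 = 1.25.
- p = 0.30, d = 0.05: OR = 0.70/0.65 = 1.08.
- p = 0.75, d = 0.15: OR = 0.25/0.10 = 2.5. This pairs the two extreme inputs of the range.

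**6. Illustration B: assessments missing in 2011-002.** Assumptions: equal true ORR of 30%; a fraction m of the 205 was not assessed and counts as non-responders; no matching. Kd27 ORR = (378 × 0.30 + 205 × 0.30 × (1 − m))/583.

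| m | Kd27 ORR | Spurious OR, Kd27 vs Kd56 |
|---|---|---|
| 25% | 27.4% | 0.88 |
| 50% | 24.7% | 0.77 |
| 100% | 19.5% | 0.56 |

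The bias can run in either direction. Illustration B also shows why a common rule that counts non-evaluable subjects as non-responders needs a completeness test beside it. At the 80% limit (m = 20%) the ORR is (113.4 + 49.2)/583 = 27.9% and the OR is (162.6/420.4)/(0.30/0.70) = 0.90.

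**7. Does the protocol deal with this elsewhere?** The limitations in Section 7.9 cover confounding, unmatched patients, the small K56 group and missing covariates, but not outcome definitions. In Appendix A, validity of outcome measurement (6.3), control of outcome misclassification (10.6) and the impact of information bias (12.1.2) are marked not applicable. Item 7.3, on information bias, is ticked but points to Section 7.3.4, which only introduces year of treatment initiation as a covariate.

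**The case against.** The strongest reply is that no difference in definition has been shown. That is correct. The trial SAPs are not available, and nothing in the protocol says that start date, censoring, denominator or assessor differs between the two sets of trials. What is shown is an exposure that the design cannot correct.

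A second reply is that outcome completeness and efficacy analysis sets are ordinary SAP content. This has some force for the completeness test. It has none for the definitions, which the protocol fixes itself; the SAP would have to contradict the protocol to harmonise them.

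Several stronger readings are tempting and are not supported:

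- *That non-evaluable subjects are dropped because nothing is imputed.* Section 7.7.2.2 does not say so. Its two sentences are best read together: endpoints arrive as derived under each trial's SAP, and nothing further is imputed. Handling may then vary by trial, which is the point made here.
- *That 2011-002 recorded no PFS or ORR and should be removed.* The Objectives column is not an inventory of data collected. Study 20140242 lists only efficacy, yet supplies 123 subjects to the safety analyses.
- *That 2011-002 makes up 35% of the matched comparison.* The figure is before matching. Table 1 gives at least 4 prior therapies for 2011-002 and 1 to 3 for the trial that supplies 463 of the 616 Kd56 subjects. Number of prior lines is in the propensity model, so many of the 205 may find no match.
- *That phase 1 heterogeneity drives the problem.* No phase 1 trial enters either primary comparison. In Table 2 the only phase 1b/2 study supplies K56, which is not compared.

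**Conclusion.** The point stands as a weakness in a stated choice. For Kd27 versus Kd56, any difference in PFS or ORR definition falls wholly on the matched hazard ratio and odds ratio; for K27 versus Kd27 it does so in part. This follows from Tables 1 and 2 and Section 7.7.2.4 without further assumption.

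The size is unknown. The odds ratio of 1.25 and the range of 1.08 to 2.5 are illustrations that assume a fully one-sided difference in denominators. If the trial definitions turn out to be the same, the bias from this source is nil.

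The completeness gap is also real, in this form: no outcome-completeness criterion governs entry to the efficacy comparisons, although the extent of missing data will be described. Whether 2011-002 has usable PFS and ORR data cannot be told from the protocol, so its removal is not warranted on present information. The change should be made before the comparisons are run.

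**What to change.** For the matched comparisons, derive both endpoints from the existing subject-level data under one rule:

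- ORR over all treated subjects, with non-evaluable counted as non-responder.
- PFS from the first carfilzomib dose, with one censoring rule.

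Show the trial-defined endpoints as a sensitivity analysis.

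Apply the 80% completeness test to PFS and ORR, trial by trial, and report the result. Only if a trial fails, drop it from the efficacy comparison and redo that propensity match. Deleting its subjects after 1:1 matching would break pairs and lose the balance that the match achieved. The safety comparisons keep all trials.

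The cost is some re-programming on datasets that Sections 7.3.5 and 7.6.2 describe as validated, small differences from reported trial results, and possibly a second match. If 2011-002 fails the test, the pools before matching fall to 378 Kd27 and 435 K27. K27 versus Kd27 then loses its only shared trial in the primary pool, so regimen becomes fully confounded with trial there too. That would have to be stated as a limitation.
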